6.8. FOLLOW-UP AFTER END-OF-TREATMENT VISIT

The date and reason of the end of study will be recorded on the patient's CRF.

After the end of treatment, all AEs and SAEs suspected to be related to PM01183 must be followed-up until recovery to grade ≤ 1 or symptoms stabilization whenever possible (for safety reporting see Section [11.2](#)). Pregnancy and suspected pregnancy occurring within six weeks from the patient's last PM01183 administration are considered immediately reportable events.

Additionally, radiological and/or clinical tumor assessments will be done during the follow-up only to those patients who discontinue treatment without documented disease progression. Patients will be followed every two months during the first six months after last tumor assessment and every three months thereafter until PD, start of other antitumor therapy, death, or study completion (clinical cut-off), whichever occurs first.

After documented progression or start of a new antitumor therapy, patients will be followed every six months, until death or study completion (clinical cut-off), whichever occurs first. For this purpose of collecting information on the patient's survival exclusively, a documented telephone call would be acceptable and no visits to the hospital will be required.

Patients who withdraw consent will not be followed with any study procedures.

6.9. STUDY COMPLETION (AS A WHOLE - CLINICAL CUT-OFF)

The planned study completion date (clinical cut-off) will be nine months after the last patient-last treatment visit in the study, or 12 months after the last evaluable patient is enrolled (whichever occurs first).

All patients on active treatment at the date of study completion will be offered to continue to receive treatment off-study according to the Investigator criteria and upon Sponsors' agreement.

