6.2. DURATION OF STUDY (PER PATIENT)

Patients will be individually evaluated at scheduled visits in up to three study periods:

- **Screening:** from signature of the ICF to first infusion of PM01183.
- **Treatment:** from first infusion of PM01183 to **end of treatment (EOT)**. **EOT** is defined as 30 days after the date of PM01183 last administration, unless the patient starts a new antitumor therapy or dies within those 30 days, in which case the date of administration of this new antitumor therapy or the date of death will be considered as EOT.
- **Follow-up:** after EOT, patients will be followed for any ongoing treatment-related AEs every four weeks until recovery to grade ≤ 1 , or until symptoms stabilization, whenever possible.

Patients will be followed for at least one year after their first infusion. Those who discontinued treatment without PD will be assessed every two months during the first six months after last tumor assessment and every three months thereafter, until

PD, start of other antitumor therapy, death, or study completion, whichever occurs first.

After documented PD or start of a new antitumor therapy, patients will be followed every six months until death or study completion, whichever occurs first. For the purpose of collecting information on the patient's survival exclusively, a documented telephone call would be acceptable.

Patients will be considered to be **on-study** from the signature of the clinical ICF to the end of the follow-up period (or screening failure).

Patients will be considered to be **on-treatment** from the date of first infusion of PM01183 until EOT.

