6.4. PATIENT REGISTRATION

After the patient has signed the ICF and upon ensuring that she meets all eligibility criteria, the patient will be entered into the trial by contacting the clinical trial monitor designated by the Sponsors and faxing the completed Patient Registration Form (Fast Fact Sheet, FFS). The FFS will be checked and eligibility confirmed by the Sponsors. A patient number will be provided to the site of enrollment within one working day. This patient number should be used on all future documentation and correspondence referring to this patient. Investigators are under no circumstances allowed to treat any patient before appropriate reception of the patient registration number, which confirms the Sponsors' agreement. Any patient treated prior to registration without the Sponsors' agreement and/or before receipt of the appropriate documentation may not be considered evaluable for the study and may need to be replaced.

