6.7. EVALUATIONS AT END OF TREATMENT

The EOT visit will be scheduled at 30 days after the last dose of study treatment (a window of \pm 7 days is allowed), unless the patient starts a new antitumor therapy or dies within those 30 days from the last dose, in which case the date of administration of this new antitumor therapy or the date of death will be considered as EOT.

For treated patients, regardless of the reason for discontinuation, if no recent data are available (i.e., within last 10 days prior to the EOT visit) or if the last data available show a grade ≥ 2 alteration, the following work-up will have to be done at this EOT visit:

- Complete physical examination, including weight (height only at baseline).
- ECOG performance status.
- Vital signs (heart rate, blood pressure, body temperature).
- Coagulation panel.
- Hematology.
- Biochemistry A.
- Biochemistry B.
- Pregnancy test, if clinically indicated.
- Electrocardiogram (ECG), if clinically indicated.
- LVEF by echocardiography (ECHO) or MUGA, if clinically indicated.
- Radiological and/or clinical tumor assessment (if not previously done and if the reason for treatment discontinuation was other than PD).
- Intercurrent events, concomitant diseases and treatments.
- Safety assessment (AEs).

Adverse events (AEs) and serious adverse events (SAEs) must be reported until 30 days after the last PM01183 administration (for safety reporting see Section [11.2](#)).

The Sponsors will evaluate all safety information that is spontaneously reported by an Investigator beyond the time frame specified in the protocol.

Patients of childbearing potential who use adequate contraception methods while on study should be reminded to continue adequate contraception for a period of six weeks after last study drug administration.

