8.1.2. Secondary Endpoints

- Duration of response (DR), defined as the time between the date when the response criteria (PR or CR, whichever is first reached) are fulfilled to the first date when PD, recurrence or death is documented.
- Clinical benefit, defined as the percentage of patients with ORR or SD > 3 months, according to RECIST v1.1.
- Progression-free survival (PFS), defined as the period of time from the date of first infusion to the date of PD, death (due to any cause), or last tumor evaluation.
- Overall survival rate at one year (1y-OS), defined as the Kaplan-Meier estimate of the probability of patients to remain alive at one year. Overall survival (OS) will be defined as time from the date of first infusion to the date of death or last contact
- Treatment safety: AEs, SAEs, and laboratory abnormalities will be graded according to the NCI-CTCAE (v4), reasons for treatment discontinuation, dose reduction and/or treatment delays.
- PK descriptive analysis and PK/PD correlation, if applicable.
- PGx expression profile of selected putative markers potentially predictive of response to PM01183, in tissues from tumor samples.

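### The clinical cut-off does not secure the promised year of follow-up, and six-monthly survival contact leaves some late-enrolled patients censored before month 12

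*Protocol*

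**What the plan says.** Protocol 6.2 (and the synopsis) sets a minimum: "Patients will be followed for at least one year after their first infusion".

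Protocol 6.9 (also 6.1 and the synopsis) sets the clinical cut-off at "nine months after the last patient-last treatment visit in the study", "or 12 months after the last evaluable patient is enrolled (whichever occurs first". Neither the last treatment visit nor the moment of enrolment is defined.

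Protocol 6.8 ends follow-up at that cut-off. After progression or a new antitumor therapy, "patients will be followed every six months, until death or study completion (clinical cut-off), whichever occurs first". A documented telephone call is accepted for survival.

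The endpoint concerned is secondary. Protocol 8.1.2 lists "Overall survival rate at one year (1y-OS), defined as the Kaplan-Meier estimate of the probability of patients to remain alive at one year". OS runs from first infusion to death or last contact (Protocol 8.1.2, SAP 6.1). The analysis is by cohort (SAP 8.9).

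**The concern.** The promise in 6.2 counts from first infusion. One limb of the cut-off counts from enrolment and the other from the end of treatment, and the earlier of the two applies. No text says that 6.2 prevails over 6.9, so the last patients in can be closed out before their year is complete.

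Separately, OS is censored at last contact, and nothing requires a contact at month 12 or at cut-off. A patient can be alive, inside the study period and past month 12, yet enter the Kaplan-Meier analysis as censored months earlier. At stake is how many patients are actually observed to the time point that defines one-year OS. With cohorts as small as 20 (A1), a few early censorings are noticeable.

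**Working it through.** **1. The plan's own duration.** Enrolment is planned at 60 months and total duration at about 72 (Protocol 6.1). 60 + 12 = 72, so the stated duration follows the 12-month limb. At the earliest, the nine-month limb gives 60 + 9 = 69 months if the last treatment visit is the last dose. If it is the end-of-treatment (EOT) visit, one month later (Protocol 6.7: "The EOT visit will be scheduled at 30 days after the last dose of study treatment"), it gives about 70.

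**2. Follow-up secured for the last patient.**
- *12-month limb:* 12 months minus the gap from enrolment to first infusion. Protocol 6.4 fixes the order: "Investigators are under no circumstances allowed to treat any patient before appropriate reception of the patient registration number". The gap is therefore never negative. If enrolment means registration, it is typically days, since most screening tests fall within 7 days of Day 1 (Table 4).
- *Nine-month limb:* suppose the last patient is also the last on treatment and stops after cycle k. Cut-off after her first infusion is 9 + (k − 1) × 21/30.4375 months, plus 30/30.4375 on the EOT-visit reading.

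| Cycles | 1 | 2 | 3 | 4 | 5 |
|---|---|---|---|---|---|
| Last-dose reading (months) | 9.0 | 9.7 | 10.4 | 11.1 | 11.8 |
| EOT-visit reading (months) | 10.0 | 10.7 | 11.4 | 12.1 | – |

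Beyond these the 12-month limb governs. The worst shortfall is about 3 months (last dose) or 2 months (EOT visit).

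**3. How often the nine-month limb governs.** It needs every patient in the study, not only the last, to be off treatment within about 3 months of last enrolment (about 2 on the EOT reading). The documents give no time on treatment, so exponential times were assumed and simulated, with 20 patients accrued over 14 months or 110 over 60 months:

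| Median time on treatment | Probability, range over both readings and both accruals |
|---|---|
| 2 months | 7–26% |
| 3 months | 0.6–4% |
| 4 months | under 1% |
| 6 months | about 0% |

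**4. The contact schedule under the 12-month limb.** The first tumor assessment is at six weeks: 42/30.4375 = 1.4 months. Count the six-monthly contacts from progression (the protocol does not say where the interval starts). Contacts then fall at 1.4 + 6 = 7.4 and 1.4 + 12 = 13.4 months. With cut-off at 12 months, a living last-enrolled patient is censored at 7.4.

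How far back does this reach? The last scheduled contact is never more than 6 months before cut-off, so anyone infused at least 18 months before cut-off is observed past month 12. Those exposed are the patients enrolled in the last 6 months of accrual. At uniform accrual that is 110/60 × 6 = 11 of about 110. Exposed does not mean lost: some die first, some have not progressed, and for some the contact dates fall well.

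**5. Expected number censored before month 12.** Simulation of 20 patients. All inputs are assumptions: uniform accrual over 14 months, exponential OS with true one-year OS of 0.5 to 0.8, median time to progression 3.5 months (none before 1.4), progression and death drawn independently, 3,000 runs.

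| Cut-off after last first infusion | Survival contact | Censored before month 12, of 20 |
|---|---|---|
| 12 months | status check at cut-off | 0 |
| 10 months | status check at cut-off | 2.0–3.1 |
| 12 months | six-monthly only | 2.5–3.5 |
| 10 months | six-monthly only | 4.2–5.8 |

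The third row shows that the contact schedule alone costs as much as a two-month-early cut-off.

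**6. Effect on the one-year OS estimate.** If deaths after the last contact also go unseen, bias is about zero; the deviations, at most 0.004, are close to the simulation error of 0.111/√3000 = 0.002. At true one-year OS of 0.5, the standard deviation is 0.111 with full follow-up, 0.116 with a 12-month cut-off and six-monthly contact, and 0.120 with a 10-month cut-off and six-monthly contact. If deaths are reported up to cut-off while survivors are censored at last contact, bias is −0.01 to −0.03.

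**The case against.** The strongest reply is that little is lost. One-year OS is a secondary Kaplan-Meier estimate in an exploratory trial, with no hypothesis or decision rule. The method does not need every patient observed to month 12. SAP Table 11.3.2.6 reports median follow-up, so short follow-up would show. The planned 72 months indicates that the sponsor expects the 12-month limb. Patients who stop treatment without progression are seen every two to three months, and those with ongoing related adverse events every four weeks, so actual last contacts may be later than the six-monthly schedule implies. All of this stands, and it keeps the consequence modest. It does not reconcile 6.2 with 6.9, and it does not supply a status check.

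Three stronger readings are tempting and should not be taken from the documents.

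- *That Cohort A1 bears the shortfall, with 4 to 5 of its 20 patients lacking month-12 status.* SAP 14.1 lists amendments of Nov 2013, Oct 2014 and Feb 2016 without saying which added A1. The SAP lists A1 only at 3.5 mg/m² (12.2.1), and Protocol 5.2.1 ties that dose to amendment no. 2, so A1 treatment is placed only at about Oct 2014 or later. Cohort A was also treated at that dose. The count itself is accrual in the last three months: 20 × 3/12 = 5.0 or 20 × 3/16 = 3.75, but 20 × 3/31 = 1.9 if accrual ran from Oct 2014 to about 2Q17. It is an upper exposure at the maximum shortfall, not an expected loss. A1 being last is an inference; late enrollees in any cohort are affected.
- *That follow-up will stop at 9.0 to 11.8 months.* This takes the last-dose reading of an undefined term and needs the unlikely condition in step 3.
- *That one-year OS will be biased downward.* No section says that deaths and alive status are collected differently. The bias is conditional on that happening in practice.

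**Conclusion.** The plan is wrong as written, with modest consequence. Sections 6.2 and 6.9 of the Protocol conflict, and nothing resolves it. The cut-off shortfall is days under the limb that will probably govern, and at most about two to three months under the other. The contact gap matters more because it operates under either limb. The 7.4-month example follows from the schedule, counting contacts from progression. The figure of 2.5 to 3.5 of 20 rests on assumed accrual, progression and survival. The likely cost is some precision in one-year OS; the small downward bias is only a possibility, and the primary ORR analysis is little affected.

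**What to change.** In Protocol 6.1, 6.9 and the synopsis, define clinical cut-off as 12 months after the first infusion of the last treated patient, and drop the earlier-of-two rule. Switching to the later of the two dates would not do, because the end would stay open while anyone remained on treatment.

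In Protocol 6.2 and 6.8 and the schedule of assessments, add a documented survival-status call for every patient not known to be dead, at month 12 and again just before cut-off. For the last patient the two coincide; record her status as at the cut-off date so that she is credited with the full 12 months.

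The cost is a cut-off days later than the present 12-month limb, or up to about three months later than the nine-month limb. That stays within the planned 72 months apart from the enrolment-to-infusion gap. The calls add one or two telephone contacts per surviving patient, a form of contact that 6.8 already accepts.

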6.10. REPLACEMENT OF PATIENTS

Patients will be replaced if they are not evaluable for the primary endpoint of the study (ORR as per RECIST v1.1), specifically (any of the following):

- They are not eligible.
- They have not been treated or have not completed at least one PM01183 infusion.
- They are not evaluable for ORR as per RECIST v1.1 and they are not categorized as "treatment failures". Treatment failures will not be replaced and are defined as patients who:
 - Discontinue treatment due to any treatment-related toxicity before an appropriate tumor assessment has been performed, or
 - Withdraw PM01183 after more than two weeks on treatment without any formal evaluation

All replaced patients will be included in the general safety analysis, if appropriate.

7. STUDY EVALUATIONS

7.1. EFFICACY

For patients to be evaluable for efficacy they must be eligible, have at least one complete infusion of PM01183, and either have at least one assessment (as per RECIST v1.1) or be categorized as “treatment failure”.

Antitumor activity will be assessed using RECIST v1.1, on a set of measurable lesions identified at baseline as target lesions and non-target lesions (if any) identified at baseline as non-target lesions and followed until PD by an appropriate method (contrast enhanced helical CT-scan, MRI, and/or clinical assessment).

Radiological and/or clinical (whenever appropriate) tumor assessment will be performed at baseline and every six weeks (two cycles) until Cycle 6 or evidence of PD. After Cycle 6, tumor assessment will be performed every nine weeks (three cycles) until evidence of PD. If an objective response is observed, according to RECIST v1.1, it must be confirmed by the same method at least four weeks after the date of the first documentation of response.

The date of response, the date of clinical or radiological PD, and the date of death will be registered and documented as appropriate.

A copy of the imaging tests conducted on the patients during this clinical trial may be requested by the Sponsor for evaluation. In addition, an independent radiological review committee may be set up, upon Sponsors' request, to review tumor assessment performed for all responding patients (partial or complete response) after study completion.

Patients will be categorized as “treatment failures” if they:

- Discontinue treatment due to any treatment-related toxicity before an appropriate tumor assessment has been performed, or
- Withdraw PM01183 after more than two weeks on treatment without any formal evaluation.

These data will be included as non-evaluable (NE) in the analysis of objective response as per RECIST v1.1, although these patients will not need to be replaced as they will be considered evaluable for efficacy.

BRCA1/2 germline mutation analysis

In patients included in Cohort B who respond to PM01183 treatment and whose BRCA 1/2 mutation status is unknown at study entry, an analysis will be performed in order to confirm or exclude deleterious germline BRCA 1/2 mutation. To this end, a blood sample will be collected at the time of response. If a BRCA 1/2 mutation is found in her sample then the patient will be analyzed along with patients included in Cohort A.

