2. OVERALL STUDY DESIGN

This is a multicenter, open-label, exploratory, phase II clinical trial evaluating the efficacy and safety of PM01183 administration to patients with previously treated MBC, as follows.

Two cohorts of MBC patients will be prospectively evaluated in the trial according to germline BRCA1/2 status (mutated [cohort A] vs. unselected [cohort B]). A third cohort (A1) will include advanced breast cancer patients with deleterious BRAC1/2 mutation who received prior treatment with poly (ADP-ribose) polymerase (PARP) inhibitors:

- Cohort A (BRCA+ cohort): At least 53 evaluable patients with previously known deleterious BRCA1/2 mutation status at study entry.
- Cohort A1 (BRCA+/PARPi cohort): 20 evaluable patients with known deleterious BRCA1/2 mutation status and prior treatment with PARP inhibitors (PARPi).
- Cohort B (unselected cohort): At least 64 evaluable patients without known deleterious BRCA1/2 mutation status at study entry, i.e., either:
 - Patients known to have no deleterious BRCA1/2 mutations (BRCA-), or
 - Patients whose BRCA 1/2 mutation status is unknown (BRCA-UK); BRCA1/2 germline mutation status will be assessed in PM01183 responding patients in this subgroup.

The primary efficacy endpoint of the study is the **overall response rate (ORR)**, defined as the percentage of patients with a response, either complete (CR) or partial (PR), according to RECIST v1.1 (Section [8.1](#)).

An interim analysis based on the primary endpoint (ORR) is planned after 20 and 30 evaluable patients have been treated in cohorts A and B, respectively (see Section [8.2](#) for details). No interim analysis is planned for cohort A1. If less than four out of 20 patients in Cohort A, or less than three out of 30 patients in Cohort B achieve an objective confirmed response, recruitment to that cohort will be terminated. Otherwise, recruitment will continue until at least 53 and 64 evaluable patients are included in cohort A and cohort B, respectively. Sample size and cohort design will be re-evaluated at this point in order to estimate the 95% confidence interval (CI) with the desired precision. Recruitment to either cohort (e.g., Cohort B) might be halted while interim analysis is being performed, if appropriate.

Patients will receive treatment in the absence of progressive disease (PD) or unacceptable toxicity for as long as it is considered to be in their own benefit (see Section [6.2.1.2](#) for details).

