3.2. SECONDARY

- To further characterize the antitumor activity of PM01183 in terms of duration of response (DR), clinical benefit [ORR or stable disease lasting over three months (SD > 3 months)], PFS, and one-year overall survival (1y-OS).
- To evaluate whether the presence of a known germline mutation in BRCA 1/2 predicts response to PM01183 in MBC patients.
- To explore the activity of PM01183 in specific breast cancer subpopulations according to hormonal receptor status, HER-2 overexpression, number and/or type of prior therapies, or according to other available histological/molecular classifications/parameters.
- To evaluate the safety profile of this PM01183 administration schedule (Day 1, q3wk) in this patient population.
- To analyze the pharmacokinetics (PK) of PM01183 in this patient population.
- To explore PK/PD (pharmacokinetic / pharmacodynamic) correlations, if applicable.
- To evaluate the pharmacogenomic (PGx) expression profile of selected putative markers potentially predictive of response to PM01183, in tissues from tumor samples.

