4. Radiological and/or clinical tumor assessment	♦ Contrast enhanced helical CT-scan or MRI (if indicated) of all measurable sites of disease involvement, as per RECIST v.1.1 (see Appendix 2). ♦ Appropriate test (radiological or clinical) of all non-measurable sites of disease.	Within 28 days prior to Day 1 of Cycle 1 ⁽⁴⁾ .
5. PGx paraffin-embedded tumor tissue ⁽⁵⁾	♦ From available prior tumor samples (primary tumor and/or metastasis). ♦ For Cohort A1 patients only: a baseline tumor biopsy.	- Archived biopsy sample from diagnosis. - Recent biopsy sample taken at any time between the end of last antitumor therapy until before first study drug infusion.
6. AEs	♦ All events should be graded as per NCI-CTCAE v4.	SAEs will be collected from the signing of the ICF.
7. BRCA1/2 germline mutation analysis	To be conducted on patients with unknown germline BRCA mutation status, who meet criteria for consideration of BRCA 1/2 genetic testing. ⁽⁶⁾	-

1. A 3-day window will be allowed for laboratory procedures, a 14-day window for radiological procedures (contrast enhanced helical CT-scan or MRI) and LVEF assessments, a 24-hour window for clinical assessments (ECOG, vital signs, ECG, weight, BSA, etc.).

2. Cardiac rhythm will be identified in ECG intervals of at least 30 seconds of duration, PR interval, QT interval (raw), heart rate (HR) and QRS complex.

3. If serum human chorionic gonadotropin (HCG) results are abnormally high, pregnancy must be clinically discarded by an additional test (i.e., US) before any other study procedure.

4. Patients with previously known CNS involvement at study entry must have documented non-PD by appropriate method.
5. Prior available stored paraffin-embedded tumor samples from the primary tumor and/or from metastases. For cohort A1 patients whose disease is not amenable to tumor biopsy, approval by the sponsor must be requested prior to inclusion. In any case, the origin of the sample must be specified: diagnosis (primary tumor or metastasis) or baseline sample.
6. National Comprehensive Cancer Network (NCCN) criteria for consideration of BRCA1/2 genetic testing (see [Appendix 3](#)).

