8.1. ENDPOINTS

8.1.1. Primary Endpoint

The primary evaluation endpoint for this phase II study is the ORR in the population evaluable for efficacy.

The ORR is defined as the percentage of patients with a confirmed response, either CR or PR, according to RECIST v1.1.

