8.2. SAMPLE SIZE

The primary endpoint for this phase II study is to evaluate ORR.

- Cohort A (BRCA+):

At least 53 evaluable patients will be recruited to test the null hypothesis that ORR is 20% or less ($p \leq 0.20$) vs. the alternative hypothesis that 40% or more patients have objective response ($p \geq 0.4$). With these assumptions, if the number of evaluable patients with objective response is ≥ 17 , then this would allow the rejection of the

null hypothesis.

- **Cohort A1 (BRAC+/PARPi):**

At least 20 evaluable patients will be for an exploratory analysis: if the number of patients responding is ≥ 4 (20%), the lower limit of the exact binomial 95% confidence interval will be higher than 5% and lack of activity in this subpopulation will be ruled out.

- **Cohort B (unselected):**

At least 64 evaluable patients will be recruited to test the null hypothesis that ORR is 10% or less ($p \leq 0.10$) vs. the alternative hypothesis that 25% or more patients have objective response ($p \geq 0.25$). With these assumptions, if the number of evaluable patients with objective response is ≥ 12 , then this would allow the rejection of the null hypothesis.

The variance of the standardized tests is based on the null hypothesis. The type I error (alpha) associated with this one-sided test is 0.025 and the type II error (beta) is <0.1 ; hence, statistical power is $> 90\%$.

Futility analyses controlled by the Gamma family boundary will be performed when 20 and 30 patients have been evaluated in cohorts A [Gm(-2)] and B [Gm(-1.5)], respectively. If less than four out of 20 patients in Cohort A, or less than three patients out of 30 in Cohort B achieve an objective response, recruitment to that cohort will be stopped. About 110 evaluable patients are expected to be included finally in the three cohorts: Cohort A (BRCA+), Cohort A1 (BRCA+/PARPi), and Cohort B (unselected).

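### Cohort B patients are reassigned to Cohort A only if they respond, which raises Cohort A's response rate and lowers Cohort B's

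*Protocol*

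**What the plan says.** Cohort B takes patients known to be BRCA-negative and patients of unknown status. For the unknown group, Protocol section 2 says "BRCA1/2 germline mutation status will be assessed in PM01183 responding patients in this subgroup". Section 7.1 defines who is tested, "In patients included in Cohort B who respond to PM01183 treatment and whose BRCA 1/2 mutation status is unknown at study entry", and when: "To this end, a blood sample will be collected at the time of response". It then gives the consequence: "If a BRCA 1/2 mutation is found in her sample then the patient will be analyzed along with patients included in Cohort A". SAP section 2 carries the same instruction in its current text.

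There is also a test before entry. Table 4 in Protocol 6.3 lists germline analysis at screening: "To be conducted on patients with unknown germline BRCA mutation status, who meet criteria for consideration of BRCA 1/2 genetic testing". This reduces the number of carriers who enter Cohort B unrecognised, but the protocol still expects some and writes a rule for them.

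The primary endpoint is a response rate in each cohort: "The ORR is defined as the percentage of patients with a confirmed response, either CR or PR, according to RECIST v1.1". Success is a responder count (Protocol 8.2, SAP 5.1): at least 17 of 53 in Cohort A against a 20% null, and at least 12 of 64 in Cohort B against a 10% null, each at one-sided alpha 0.025. One secondary objective is "To evaluate whether the presence of a known germline mutation in BRCA 1/2 predicts response to PM01183 in MBC patients". Protocol 8.3.1 compares the cohorts by Fisher's test and logistic regression.

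**The concern.** Cohort membership should be fixed by something known before the outcome. Here it depends on the outcome itself. A hidden carrier in Cohort B who responds is found, adds one to both numerator and denominator of Cohort A, and leaves Cohort B. A hidden carrier who does not respond is not sampled and remains a Cohort B failure. The transferred group has a 100% response rate by construction.

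Three results are exposed: Cohort A's test of the 20% null, Cohort B's test of the 10% null, and the comparison that asks whether BRCA mutation goes with response. The bias in that comparison runs towards the trial's own hypothesis and is present even if BRCA status has no effect. Because success is defined by counts, a single transferred patient can decide either cohort.

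**Working it through.** **Inputs from the documents.** Cohort A: n = 53, null 0.20, alternative 0.40, success at 17 or more, stop if fewer than 4 of the first 20 respond. Cohort B: n = 64, null 0.10, alternative 0.25, success at 12 or more (Protocol 8.2).

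**Assumption.** Let q be the share of Cohort B patients who are undetected carriers. The documents do not give it. Protocol 1.1 puts hereditary BRCA disease at 5–10% of all breast cancers. I use 3%, 5% and 10%, where the low end allows for screening tests. Carriers are taken to respond at the Cohort A rate.

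**Reproducing the design.** The critical count on the null-variance normal test is n·p0 + 1.96·√(n·p0·(1−p0)).

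- A: 10.6 + 1.96·√8.48 = 16.31, so 17.
- B: 6.4 + 1.96·√5.76 = 11.10, so 12.

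Exact power with the futility rules is 0.901 (A) and 0.903 (B). The stated design is reproduced.

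**One transfer at the boundary.** Here z = (x − n·p0)/√(n·p0·(1−p0)).

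| | Before | After |
|---|---|---|
| Cohort A | 16/53 = 30.2%, z = 1.85, fails | 17/54 = 31.5%, z = 2.11, meets 17 |
| Cohort B | 12/64 = 18.8%, z = 2.33, succeeds | 11/63 = 17.5%, z = 1.97, misses 12 |

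**Cohort A type I error with k transfers.** The exact two-stage probability at response rate 0.20 is Σ over x = 4 to 20 of P(Bin(20, 0.20) = x) × P(Bin(33, 0.20) ≥ 17 − k − x). Transfers are not counted at the interim.

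- k = 0: 0.0252
- k = 1: 0.0491
- k = 2: 0.0880

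**Averaged over the number of transfers.** k follows Bin(64, q × 0.20).

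| q | Expected transfers | Cohort A type I error |
|---|---|---|
| 3% | 64 × 0.03 × 0.20 = 0.38 | 3.6% |
| 5% | 0.64 | 4.4% |
| 10% | 1.28 | 6.9% |

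**False difference between cohorts.** Suppose everyone responds at 20%. Cohort A's expected ORR is the mean of (10.6 + k)/(53 + k). Cohort B's is (1 − q)·0.20/(1 − 0.20q).

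- q = 5%: 20.9% against 19.2%, a gap of 1.7 points.
- q = 10%: 21.9% against 18.4%, a gap of 3.5 points.

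**Cohort B power.** Take ORR 25% in non-carriers and 40% in carriers, keep the count of 12, and ignore the interim. As enrolled, responders follow Bin(64, 0.25(1 − q) + 0.40q). After transfers, those left follow Bin(64, 0.25(1 − q)).

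| q | Power as enrolled | Power after transfers |
|---|---|---|
| 3% | 0.919 | 0.882 |
| 5% | 0.927 | 0.863 |
| 10% | 0.944 | 0.805 |

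**The case against.** The best counter-argument concerns size.

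- **Cohort B cut-off.** The plan's test is a standardized one. If the cut-off is recomputed at n = 63, it is 6.3 + 1.96·√5.67 = 10.97, so 11/63 would still reject. On that basis Cohort B's power is 0.911, 0.907 and 0.877 at 3%, 5% and 10% carriers, against a design value of 0.907 without the interim. This stands as a qualification. However, neither document provides for recomputing, the stated count is 12, and the exact one-sided p-value for 11/63 is 0.047.
- **Smaller pool.** The protocol expects about 110 evaluable patients in three cohorts, which leaves about 37 for Cohort B after 53 and 20. The SAP's safety groups (12.2.1, 12.4) list no Cohort B patients at 3.5 mg/m². With 37 patients, Cohort A's type I error would be 3.1%, 3.5% and 4.7%. The text still calls for at least 64, so both sets of figures are worth having.
- **Fewer carriers.** Cohort B excludes known carriers, its known BRCA-negative patients cannot move, and the NCCN criteria in Appendix 3 are broad. Ten percent is therefore a worst case. At 1–2% of 64, the type I error is 2.8–3.2%.
- **Scope.** Neither document says whether the transfer governs the success counts, the interim counts or only a further analysis, and the trial and the between-cohort comparison are labelled exploratory. But nothing limits the rule to a secondary analysis, and the trial sets formal hypotheses with success counts.

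These points reduce the magnitude. They do not change the direction, and no as-enrolled or sensitivity analysis in either document offsets it.

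**Conclusion.** The concern holds. Selection on the primary outcome is written into both documents, and its direction is certain once any mutated responder is found; if none is found, nothing changes. The Cohort A flip at 16/53 holds both on the stated count and on the plan's own z-test at the new denominator. The Cohort B flip holds on the stated count of 12 only.

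The size rests on the unknown carrier share and on how many patients Cohort B enrols. Across the cases examined, Cohort A's type I error lies between 2.8% (1% carriers among 64) and 6.9% (10% among 64). One actual transfer nearly doubles it, from 2.5% to 4.9%. Because the rule affects the primary endpoint, favours the BRCA hypothesis and is cheap to remove, it should be corrected before analysis.

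**What to change.** Delete the transfer sentence in Protocol 7.1 and SAP section 2 and put in its place:

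> All efficacy analyses, including the 17/53 and 12/64 decisions, the interim counts and every comparison of Cohort A with Cohort B, use the cohort assigned from BRCA status known at study entry. Mutations found later in Cohort B responders are reported descriptively and do not change cohort assignment.

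Restrict the analysis of whether BRCA mutation predicts response to patients whose status was determined independently of response. If the sponsor wants to show the reassigned result, label it as a sensitivity analysis.

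The cost is one sentence in each document, with no extra patients or tests, and the design error rates are restored. Cohort A may report one or two fewer responders.

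The alternative is to genotype every BRCA-unknown Cohort B patient whether or not she responds, and move all carriers. That also removes the selection, but it needs more testing, and the sample sizes and cut-offs would have to be reset.
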